by applying brief stimuli well below the participant's tolerance level. Due to the thermal stimulation procedure, there is a slight change of burning the skin. However, this risk is diminished by carefully monitoring the stimuli levels. The risk of burn injury as a result of overheating contact thermode due to technical malfunction is very unlikely because the subject: (1) is free to withdraw from the thermode; (2) has the option to stop the stimulus at any point. In addition, the stimulator incorporates automatic safety features that do not depend on actions of the investigator or subject: (3) a safe range (max 520C) is programmed into the system preventing accidental use of potentially harmful temperature set-points; (4) the software continuously monitors thermode temperature and automatically interrupts thermode contact with the skin when the process value exceeds the set-point by >1.00 C.

There is also a minor risk of psychological discomfort due to QST. The prospect of being subjected to painful stimulation in an unfamiliar location, surrounded by unfamiliar investigators and equipment that may look intimidating may lead to anxiety. We try to minimize this anxiety by thoroughly explaining all procedures and taking the time to answer all questions the participant might have. We make sure that ample time is scheduled for the first session, so the participant does not feel rushed and has time to get to know the lab environment and investigators. In addition, we allow the participant to experience a few sample stimuli before deciding whether or not to go ahead with the actual testing. Our tests always start with a few non-nociceptive stimuli before the temperature rises gradually. In spite of these measures we cannot completely rule out that some participants may feel some anxiety during the first session. However, based upon experience in other studies using similar protocols, we are confident that most subjects will not experience psychological stress during the second and subsequent sessions, when they have become familiar with the experimental setting.

Clinical Pain, Psychological, and Function Measures: The questionnaires and functional tasks proposed in this study are considered minimal risk. Some individuals may feel unconformable with some questions. Notably, the PROMIS short for screening for anxiety and depression may indicate that a research subject is anxious or depressed. These forms will be scored prior to the completion of the session. An elevated score, meaning an individual is anxious and/or depressed will be handled by contacting one of the clinical co-Investigators ([name] or [name]) and obtaining the appropriate referrals.

Radiation Exposure. There is an extremely small chance that research subjects will be more susceptible to developing cancer because of increased exposure to radiation experienced during the radiographs required for this study. However, the risk due to exposing the hand, a distal segment that is not close to vital organs, to the radiation from an x-ray is extremely low. The Food and Drug Administration (FDA) Guidelines for Research Subjects sets an estimated dose equivalent (EDE) limit of 3 rem for a single session and no more than 5 rem annually. The total EDE associated with participation in this study is estimated to be less than 2 mrem (note the difference in units). This is less than 1 percent of the amount of background radiation that the average person in the United States receives each year (annual background radiation estimated to be 0.36 rem).

Additional Protections Against Risk:

The study design provides several measures to minimize the potential risks to subjects:

Minimizing Risks to Privacy by Protecting Confidentiality: The collected PHI includes, age and biological sex. This information will only be identifiable by a subject specific code. A document linking the subject specific code to the name of the subject will be stored securely in a locked cabinet within [name] laboratory and/or electronically on a password-protected

server in the University of Florida. Only IRB approved research personnel will have access to identifiable research data.

Minimizing Risks by Using Qualified Study Personnel

We will also protect subjects by having appropriately trained personnel perform/oversee the necessary procedures. The radiographs will be acquired at UF Health in a manner identical to that used on patients, such that privacy and safety will be ensured. Trained and qualified technicians employed by the University of Florida will obtain all scans.

Motion analysis and EMG testing (Session I biomechanics testing) will take place in [name] Biomechanical Laboratory in the J. Crayton Pruitt Family Department of Biomedical Engineering. Only trained members of the research team will operate the motion capture and EMG systems. [name] has received training on insertion of fine wire EMG electrodes through the Gait & Clinical Movement Analysis short course. This training fulfills the classroom training requirements for clinicians and researchers in California, the state with the strictest fine wire EMG electrode laws. All fine wire needle electrodes will be placed following best practices to ensure safety and sterility.

The experimental pain procedures (Session II somatosensory testing) described in this application are widely used and safe. While they produce pain, risks to the subjects are minimal, because:

- 1) the pain is transient in nature, and generally subsides immediately after the procedure;
- 2) subjects are instructed that they may stop any procedure at any time with no adverse consequences; and
- 3) the level of pain experienced by subjects is below their tolerance level.

[name], who has extensive experience with experimental pain testing, and [name], who has extensive experience with clinical pain testing, will ensure all pain testing is completed in a safe and appropriate manner. Risks will also be minimized by adhering to our exclusion criteria, and the study physician ([name], co-mentor) will have full discretion to exclude participants for whom they feel there is excessive risk for participation.

8. POSSIBLE BENEFITS:

There are no direct benefits to subjects for participating in this study. However, the knowledge gained from this study will benefit society by providing new information regarding the mechanisms underlying CMC OA pain and disability.

The contribution of this proposal is expected to be improved understanding of how biomechanical, neuromuscular, and somatosensory mechanisms influence symptom severity in adults with CMC OA. This contribution is important as it directly addresses the primary barrier preventing the design of new, optimal treatments: the mechanisms that influence the severity of CMC OA have not been fully identified, and therefore cannot be clinically targeted. The data collected from this study will also form the foundation for future work on CMC OA phenotypes. Thus, this study will enable future design and development of effective, targeted treatment for CMC OA.

9. CONFLICT OF INTEREST:

The investigators do not have any conflicts of interest

References:

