Aim 2. Quantify the relationship between function, pain symptomology, and disease severity. Hand function, clinical and experimental pain, and disease severity will be measured in adults with end-stage CMC OA, age-matched controls, and young-healthy individuals. We *hypothesize* individuals with CMC OA will demonstrate greater functional deficits and higher experimental pain sensitivity than age-matched controls and young-healthy individuals. Additionally, in individuals with CMC OA, we hypothesize that functional loss will be associated with higher clinical pain, but not necessarily higher disease severity. Completion of this aim will comprehensively and quantitatively characterize the multi-faceted symptomology of CMC OA and provide insights into the somatosensory mechanisms affecting this disease.

6. RESEARCH PLAN:

Sample Size & Justification: A total of 60 subjects will complete the proposed research study: 20 individuals with end-stage CMC OA, 20 age-matched controls, and 20 young-healthy individuals. These subjects will represent the racial and ethnic diversity of the state of Florida. Vulnerable populations including pregnant women and prisoners will be excluded. All subjects will be between the ages of 18 to 90. Specifically, the end-stage CMC OA cohort and age-matched controls will be between the ages of 40 to 90 as CMC OA is most prevalent in older adults. While the young-healthy cohort will be between the ages of 18-39. A power analysis ($\alpha = 0.05$, $1-\beta = 0.80$) to detect 20% differences in pinch strength between groups required 15 individuals per cohort. Due to including a young-healthy cohort and to prevent erroneous inferences to occurs after multiple comparisons, 20 individuals per cohort will be recruited. Note, pinch strength was the only relevant variable for which standard deviations could be consistently estimated from the literature.^{23, 36} Thus, an important outcome of this pilot project will be the data necessary to robustly estimate sample sizes for future studies. For reference, prior studies indicate that individuals with early-stage CMC OA have 20-30% less pinch strength than controls.^{23, 36}

A summary of inclusion and exclusion criteria are provided below:

Inclusion Criteria:

CMC OA Subjects:

- female between the age of 40 to 90 years
- end-stage CMC OA diagnosed by a board-certified clinician

Age-Matched Control:

- female between the age of 40 to 90 years
- no joint or muscle pain in the hand or wrist

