If a potential participant answers "yes" to question (a) – (b) and "no" to questions (c) – (f), then we will ask the following follow-up question: "What kind of arthritis have you been diagnosed with in your hand or wrist?" If the answer is thumb OA, we will proceed with scheduling a study visit as an CMC OA subject.

Otherwise, the potential participant will be informed that he or she is ineligible to participate.

To facilitate continued communication and follow-up, we will ask the potential participant what his or her preferred method of contact is and will record his or her name, phone number, and e-mail address during these initial conversations. We will use the e-mail address to provide the potential participant with an electronic copy of the informed consent form to review prior to his or her first visit. This copy of the informed consent form will be provided to the subject at least 24 hours prior to their scheduled participation. All research subjects will be consented in-person at the time of their first study session.

Enrollment & Informed Consent:

Prior to experimental data collection, each participant will be given the opportunity to review the informed consent form and study procedures in-person with a member of the study team. This discussion will include information on study purpose and procedures, benefits and risks, who to contact (study team, IRB, etc.), that participation is voluntary and participants can withdraw at any time, HIPAA and confidentiality, as well as cost and compensation. The participant will be given the opportunity to ask questions. After all questions have been answered, the participant will sign the informed consent form, documenting that they provide consent to participate as well as authorization to access their private health information as outlined on the informed consent form.

Research Approach:

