The proposed human subject research will occur during three sessions. The first session (focused on biomechanics data for Aim 1) will include motion capture, electromyography (EMG), movement-evoked pain testing. This session is expected to last no more than 4-hours. The second session (focused on somatosensory data for Aim 2) will include experimental pain testing, clinical pain testing, and clinical outcome measures. If needed, the clinical outcome measures can be completed in the first session as it is at no risk to the patient or the study. This session is expected to last 2-hours. The third session (medical imaging for Aim 2) will involve recording plain film radiographs. This session is expected to last less than 1-hour. Sessions can be scheduled consecutively on the same day or as separate study visits, based on the subject's schedule and availability. Sessions can also be completed in any order. Detailed descriptions of each session is provided below:

Session I – Biomechanics Testing Session (Collection of Data for Aim 1).

Location: All biomechanics testing will occur in [name] Biomechanics Laboratory, located in Room 510 of the New Engineering Building ([name]). This laboratory is specifically designed for biomechanical testing and human subject experiments. It is a limited-access lab, meaning that only [name] students and collaborators have access. All individuals with access have completed human subjects research training. During testing, only members of the IRB-approved Study Team will be involved in experimental data collection. A sign that reads "Experiment in Progress" will be posted on the door during data collection to ensure subject privacy is maintained.

Testing Procedures: All participants will be asked to wear short sleeve or sleeveless tops during testing. Participants will have the option to wear their own clothing or clothing provided by the lab. Participants will also be given the option to change into clothing in a private changing area after arrival at the lab.

Upon arriving at the Musculoskeletal Biomechanics Lab, participants will be asked to provide basic demographic (age and sex) and anthropometric (height, weight, limb length) data. Following collection of this information, biomechanical data will be collected using skin-marker motion capture, electromyography (EMG), and movement-evoked pain testing.

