During testing, participants will be asked to perform range of motion tasks (e.g., circumduction of the CMC joint) as well as strength tasks (e.g., lateral pinch and opposition pinch) at varying effort levels (maximal and sub-maximal). Each task and effort level will be repeated at least twice. Skin-marker motion capture, EMG, and movement-evoked pain data will be collected during each task as described below:

Skin-Marker Motion Capture & Force Sensors

Skin-marker motion capture involves placing reflective markers on palpable boney landmarks, such as the distal radial styloid. These reflective markers are secured to the subject's skin using adhesive tape. Reflective markers will be placed across the hand and arm following the guidelines of the International Society of Biomechanics. Locations of the markers will be recorded during completion of the tasks using a 12-camera Vicon Vero motion capture system. During testing, the forces produced by the thumb will be recorded using custom force sensors. These data will provide a kinematic description of how the thumb, wrist, and arm move during the recorded tasks as well as kinetic data describing the forces produced. These data will also be used in the musculoskeletal simulations to calculate CMC joint contact forces.

Intramuscular and Surface Electromyography (EMG).

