Most of the experimental procedures involved in this study have no greater than minimal risks. However, intramuscular electromyography (EMG), which involves insertion of fine wire needle electrodes, poses slightly more than minimal risk. All procedures are described below:

Activities Performed During Motion Capture. Participation in the motion capture study should not cause pain or discomfort beyond what is experienced in routine, daily life or a standard clinical evaluation during a visit to the doctor. Nonetheless, we will exclude research subjects who are unwilling or unable to perform the activities to ensure that it poses no substantial additional risk or causes no substantial pain to our subjects.

Skin-Marker Motion Analysis. Skin-marker motion analysis poses minimal risk to subjects. Reflective markers are secured to the skin using adhesive tape. Removing this tape may cause mild discomfort or skin irritation (i.e., redness). This discomfort is similar to that experienced when removing a bandaid.

EMG. Surface EMG poses minimal risk. The only known health risk is mild discomfort or skin irritation (i.e., redness) associated with removal of the surface electrodes. Rare, but possible risks of intramuscular (or fine wire) EMG include inflammation, infection, bleeding, and/or fainting. Damage to nerve or blood vessels from the wire is also possible, although rare. Mild discomfort associated with placement of the intramuscular EMG electrode is possible. We will minimize risks by having only trained research staff insert intramuscular electrodes. Ultrasound guidance will also be utilized to assist with needle placement around sensitive anatomy. Additionally, subjects will be given the option of stopping needle insertion at any time. Subjects will be fully compensated for the biomechanics session, even if they choose to stop EMG needle insertion prior to all electrodes being placed.

Quantitative Sensory Testing. QST is generally considered safe. However, participants will experience some pain or discomfort. Due to the pressure pain procedure (mechanical stimuli), there is a slight chance that a bruise may form as a result of the pressure pain procedure. Also, some patients may experience after-sensations after application of pressure stimuli to their symptomatic thumb, though this is expected to be brief in duration. Also, this risk is diminished

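### Does using 20 per cohort both as the number recruited and as the number completing leave the trial short of subjects?

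*Protocol*

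**What the plan says.** All figures are in the Protocol, section 6 (Research Plan), Sample Size & Justification. The paragraph opens with the number finishing: "A total of 60 subjects will complete the proposed research study: 20 individuals with end-stage CMC OA", plus 20 age-matched controls and 20 young-healthy individuals. The calculation, at alpha 0.05 and power 0.80, was made "to detect 20% differences in pinch strength between groups required 15 individuals per cohort". The rise to 20 is explained in one sentence: "Due to including a young-healthy cohort and to prevent erroneous inferences to occurs after multiple comparisons, 20 individuals per cohort will be recruited". The same paragraph calls the study a pilot that is to supply data for sizing later work.

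Other parts of the protocol provide for losses:

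- Section 6, Initial Contact with Study Team: "All research subjects will be consented in-person at the time of their first study session".
- Section 6, Enrollment & Informed Consent: subjects are told that "participation is voluntary and participants can withdraw at any time".
- Section 6, Research Approach: "Sessions can be scheduled consecutively on the same day or as separate study visits".
- Section 7, Activities Performed During Motion Capture: "we will exclude research subjects who are unwilling or unable to perform the activities". In Session I these activities include "strength tasks (e.g., lateral pinch and opposition pinch) at varying effort levels (maximal and sub-maximal").
- Section 7 also lets subjects try sample stimuli before agreeing to sensory testing, and gives the study physician discretion to exclude.

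The document gives no loss rate, over-recruitment figure or replacement rule.

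**The concern.** One number serves two quantities. If 20 per cohort are recruited and 20 per cohort complete, loss after consent must be zero, yet the protocol describes several ways to lose subjects. The five subjects added to the 15 look like a cushion, but the stated reasons for them are the third cohort and multiplicity. If multiplicity takes all five, any loss comes out of the power.

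The exclusion for inability to do the tasks also acts on pinch strength, the variable the trial was sized on. If it fell mainly on the weakest hands in the CMC OA cohort (an inference; the protocol does not say so), it would also shrink the observed difference between cohorts. At stake would be a study that stops at 60 consented, finishes with fewer, and has less than its intended power.

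**Working it through.** **Inputs.** From the sample-size paragraph: alpha 0.05, power 0.80, a 20% difference in pinch strength, 15 per cohort before the increase, 20 after. Not given: the standard deviation, whether the test is one- or two-sided, the number of comparisons, the adjustment method and the loss rate. I assume two-sided two-sample t tests and solve for the standardised difference d.

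**Step 1: d from the protocol's 15.** Power is exactly 0.80 at 15 per cohort when d = 1.060, and exactly 0.80 at 14 per cohort when d = 1.100. A requirement rounded up to 15 therefore implies d between 1.06 and 1.10. For a 20% difference that is a coefficient of variation of 0.20/1.10 = 18% to 0.20/1.06 = 19%. The 15 cannot be checked further without the standard deviation.

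**Step 2: from 15 to 20.** In the normal approximation the standard deviation cancels. For m comparisons with a Bonferroni split, n = 15 × [(z(1 − 0.05/(2m)) + z(0.80)) / (z(0.975) + z(0.80))]².

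- m = 3: [(2.394 + 0.842)/(1.960 + 0.842)]² = 1.334, and 15 × 1.334 = 20.0.
- m = 2: [(2.241 + 0.842)/(1.960 + 0.842)]² = 1.211, and 15 × 1.211 = 18.2.

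Three comparisons reproduce the protocol's 20. The protocol does not say that this is how 20 was reached. By the exact t calculation, 80% power needs 19-21 per cohort for three comparisons and 18-19 for two.

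**Step 3: power after losses, 20% difference, d = 1.06 to 1.10.**

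| Completers per cohort | Alpha 0.05/3 | Alpha 0.05/2 | Alpha 0.05 (as stated) |
|---|---|---|---|
| 20 | 0.797-0.830 | 0.841-0.869 | 0.904-0.924 |
| 19 | 0.771-0.805 | 0.819-0.848 | 0.888-0.910 |
| 18 | 0.742-0.778 | 0.794-0.825 | 0.870-0.894 |
| 16 | 0.677-0.715 | 0.736-0.770 | 0.827-0.853 |
| 15 | 0.640-0.679 | 0.702-0.737 | 0.800-0.828 |

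Tukey's method for three groups lies close to the two-comparison column: about 0.82-0.85 at 20 and 0.78-0.81 at 18. If only the CMC OA cohort loses subjects, power at 0.05/3 is 0.769-0.804 with 18 against 20, and 0.736-0.772 with 16 against 20. One-sided tests at 0.05/3 (d = 0.931 to 0.965) give 0.766-0.797 at 20 and 0.716-0.749 at 18.

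**Step 4: larger differences.** The protocol cites pinch strength 20-30% below controls in early-stage disease; this cohort is end-stage. With the same standard deviation, a 25% difference multiplies d by 1.25 and a 30% difference by 1.5. At 0.05/3 with only 16 per cohort, power is then 0.88-0.90 and 0.97-0.98.

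**Step 5: what a loss allowance would mean.** Recruits per cohort for 20 expected completers = 20/(1 − loss), rounded up. For assumed losses of 5, 10, 15 and 20% this gives 22, 23, 24 and 25 per cohort, or 66, 69, 72 and 75 in all. With 60 recruits, the chance that all complete is 0.95^60 = 4.6% at 5% loss and 0.90^60 = 0.2% at 10%.

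**The case for a change.** The strongest case for acting is that the double use of 20 is plain in the text and needs no assumption about standard deviation or method. Recruitment and completion targets belong in a protocol, and both are stated here, with the same number. Any loss breaks one of the two statements, and at a loss of even 5% it is unlikely that all 60 recruits complete. Every adjusted reading tried leaves at most about three spare per cohort. Only an unadjusted analysis tolerates a loss of five, and that sits badly with multiplicity being a stated reason for the increase.

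The inconsistency in wording stands, and so does the point that the five extra subjects were not added for losses. The claim of harm is weaker, for four reasons.

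- It needs enrolment to stop at 60 consented. The protocol sets no such cap, and the paragraph's opening commitment is to completers.
- It needs three comparisons and a Bonferroni-type split. Neither is stated, and the Aim 2 group hypothesis names only two contrasts, CMC OA against each other cohort.
- Failing to complete the study is not the same as losing pinch data. Pinch is measured in Session I and again among the functional outcome measures, so a subject who declines sensory testing or misses imaging may still contribute it.
- A one-subject loss cannot be told apart from the uncertainty in d: the smallest adequate number for three comparisons is itself 19-21.

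That exclusions would fall on the weakest hands is possible, but nothing in the document supports or sizes it.

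**Conclusion.** No change is called for. The sentence is loosely worded, but 20 per cohort is a sound number to analyse and no stated figure is shown to be missed. The stated power of 80% at alpha 0.05 with 15 per cohort still holds, at 0.80-0.83, after five per cohort are lost. The shortfall appears only under an assumed correction. With three Bonferroni comparisons and two lost per cohort, power is 0.74-0.78 for a difference at the bottom of the range the protocol cites; with two comparisons and the same loss it is 0.79-0.83.

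The available remedies add little. One is to write down that recruitment continues until 20 per cohort have completed, which the text already allows and a study team would sensibly do. The other is to consent 6-15 more subjects on a loss rate that nobody has stated, which exposes more people to fine-wire electrodes, pain testing and x-rays. In a pilot with short participation, whose clinical pain metrics rather than pinch strength are named as primary outcomes, losing one or two subjects per cohort would still leave sound conclusions. This rests on two-sided t tests, d solved from the protocol's 15, and losses of that order. Much heavier losses, or losses concentrated in the CMC OA cohort, would matter more, but the document gives no ground to expect them.

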Young-Healthy Subjects:

- female between the age of 18 to 39 years
- no joint or muscle pain in the hand or wrist

Exclusion Criteria:

All Groups:

- Pregnant women; minors (under age 18); mentally disabled; any persons incarcerated, on parole, on probation, or awaiting trial
- Individuals with concomitant musculoskeletal pathologies (other than osteoarthritis) in the hand or wrist, including distal radius fracture, contracture, trigger finger, and carpal tunnel
- Individuals with history of uncontrolled diabetes, rheumatoid arthritis, muscular dysfunction, or neurological disease

Recruitment:

The CMC OA subjects, age-matched control subjects, and young-healthy control subjects will be recruited, as described below:

CMC OA Subject Recruitment: Subjects with CMC OA will be recruited directly from the hand clinics at the UF Orthopaedics Sports Medicine Institute (OSMI). Specifically, a clinical member of the study team affiliated with the Department of Orthopaedics (e.g., [name]) will identify individuals who meet the inclusion criteria. These individuals will be asked at the end of their clinic visit if they are interested in learning more about the research study and potentially participating. At this time, the potential participant's contact information (name, e-mail, phone number) and preferred contact method (phone or e-mail) will be recorded. A member of the IRB-approved study team will then reach out to the potential participant by phone or e-mail to discuss the study and answer any questions. If the potential participant expresses interest, he or she will be e-mailed a copy of the informed consent document to review and discuss with their friends and/or family. The study sessions will also be scheduled at this time. Subjects will be consented in-person at the time of their first study session.

Age-Matched Control Subjects and Young-Healthy Subjects: Age-matched control subjects and young-healthy subjects will be recruited using the mechanisms listed below. It should be noted that individuals with CMC OA may also contact the study team via these mechanisms. However, the study team anticipates that these mechanisms will more readily identify age-matched control subjects:

- 1) Recruitment Flyer – An IRB-approved recruitment flyer will be posted around the University of Florida's campus and the Gainesville community in approved advertising

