locations. The flyer will provide potential participants with the information necessary to contact the Study Team by phone and/or e-mail.

- 2) Website Advertisement – An IRB-approved recruitment message will be posted on the Principal Investigator's Lab Website (<https://www.bme.ufl.edu/labs/[name]/get-involved/>) The recruitment message will provide potential participants with the information necessary to contact the Study Team by phone and/or e-mail.
- 3) Word of Mouth – The Principal Investigator and Study Team frequently share results from completed studies through invited talks, guest lectures in undergraduate and graduate courses, and community events. When discussing our human subjects research, one of the most commonly asked questions is whether there are opportunities to become involved as a study participant. Thus, we will share information about the study verbally with interested members of the community. When such verbal conversations take place, we will provide the potential participants with the information necessary to contact the Study Team by phone and/or e-mail. Scheduling and enrollment will occur at least 48 hours after the initial conversation and only after the potential participant has proactively contacted the Study Team.

Initial Contact with Study Team:

When a potential participant contacts the Study Team, we will follow-up with the potential participant by phone or e-mail. During that discussion, we will ask the following questions:

- a) Are you a female between 18 and 90 years old?
- b) Have you been diagnosed with arthritis in your hand or wrist?
- c) Do you currently have muscle or joint pain in the hand or wrist?
- d) Have you had any muscle or joint pain in your hand or wrist requiring medical attention or physical therapy in the last 6 months?
- e) Are you currently pregnant, mentally disabled, incarcerated, on parole, on probation, or awaiting trial?
- f) Do you have any systemic musculoskeletal, neurological, or autoimmune diseases, such as diabetes, rheumatoid arthritis, or stroke?

If a potential participant answers "yes" to question (a) and "no" to questions (b) – (f), then we will proceed with scheduling a study visit as an age-matched control subject.

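### The initial-contact script contradicts the eligibility criteria on age and on diabetes and autoimmune disease, and may leave cases and controls under different diabetes rules

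*Protocol*

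**What the plan says.** All references are to Protocol section 6, Research Plan, unless stated.

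- **Criteria.** For CMC OA subjects and age-matched controls the age criterion is "female between the age of 40 to 90 years". Young-healthy subjects are women aged 18 to 39. The exclusions headed for all groups name diabetes only where it is uncontrolled, and among autoimmune diseases name only rheumatoid arthritis.
- **Routes.** CMC OA subjects come mainly from the hand clinics, where a clinical team member identifies them against the inclusion criteria. For the other two cohorts, "Age-matched control subjects and young-healthy subjects will be recruited using the mechanisms listed below": flyer, website and word of mouth. People with CMC OA may also respond this way.
- **Script.** Under Initial Contact with Study Team, "When a potential participant contacts the Study Team, we will follow-up with the potential participant by phone or e-mail". Question (a) is "Are you a female between 18 and 90 years old". Question (f) is "Do you have any systemic musculoskeletal, neurological, or autoimmune diseases, such as diabetes, rheumatoid arthritis, or stroke".
- **Outcomes.** With yes to (a) and no to (b) through (f), "then we will proceed with scheduling a study visit as an age-matched control subject". With yes to (a) and (b) and no to the rest, the caller is asked which arthritis she has: "If the answer is thumb OA, we will proceed with scheduling a study visit as an CMC OA subject". For everyone else: "Otherwise, the potential participant will be informed that he or she is ineligible to participate".

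**The concern.** The script is the operating instruction that staff follow on the telephone. Where it departs from the criteria, it decides who is booked and under which cohort label. Two departures are plain from the text.

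The first is age. One cohort of three has no exit from the script that serves it, and neither booking branch applies the lower limit of 40.

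The second is diabetes and autoimmune disease. The script is stricter than the exclusion list, so volunteers whom the criteria admit are told that they are ineligible.

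The second departure may also act unequally. The script is written for people who contact the team, which means nearly all controls but only some cases. Session II uses sensory testing to measure nerve fiber function, and Aim 2 (section 5) compares experimental pain sensitivity between CMC OA subjects and controls. A diabetes rule that differs between the two groups bears on that comparison. The Aim 1 association between pain and movement, and the Aim 2 hypothesis within CMC OA subjects, are not in question.

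**Working it through.** No stated figure is at issue. The check follows each kind of caller through the script and compares the result with the criteria.

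| Caller | Criteria | Script |
|---|---|---|
| Woman of 25, no to (b) to (f) | Young-healthy | Age-matched control |
| Woman of 60, no to (b) to (f) | Age-matched control | Age-matched control |
| Woman of 35 with thumb OA, no to (c) to (f) | Too young for the CMC OA cohort | Booked as CMC OA subject |
| Woman of 60, controlled diabetes, no pain or arthritis | Not excluded | Ineligible |
| Woman of 60, autoimmune disease that is neither rheumatoid arthritis nor covered by another exclusion | Not excluded | Ineligible |

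Only the second row agrees.

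**Reach of the age gap.** The young-healthy cohort is 20 of 60 subjects, one third of the study, and the script serves its only described route. Women of 18 to 39 do pass the script. What is missing is the correct cohort label.

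**Can it be corrected later?** Age is recorded in Session I, so a wrong label could be noticed. The protocol describes no step that reassigns a subject, and it lets sessions occur in any order, so Session I need not come first. A caller turned away at question (f) is not seen again.

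**Does the diabetes rule differ by route?** The script begins when a person contacts the team. For clinic subjects it is the team that makes contact, to discuss the study. The protocol does not say whether question (f) is asked then. There are two readings:

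- If it is asked, the rule is the same for both groups, but stricter than the criteria.
- If it is not, controlled diabetes may enter the CMC OA cohort through the clinic but cannot enter the control cohorts.

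**Age-matched.** The only link stated between the ages of cases and controls is the shared range. No pairing, stratum or frequency rule is given. Two groups whose mean ages differ by anything up to 90 − 40 = 50 years would satisfy the criteria. That is a logical bound and not an expected gap.

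**The case against.** The strongest reply is that the script is only a pre-screen. It accepts a self-reported diagnosis where the criteria require a clinician's, and it does not ask by name about fracture, trigger finger or carpal tunnel. The inclusion criteria still define the groups, age is recorded, and the intent to recruit young-healthy subjects by this route is clear. This stands to the extent that the age gap is a routing error and not in itself a source of confounding. It does not remove the contradiction, because no later eligibility check is described and rejected callers are lost.

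On diabetes, the difference between cases and controls is inferred from silence, and the exclusions are headed for all groups. That also stands, so the point is put conditionally. A reader might go further and infer that the asymmetry inflates false support for Aim 2. The document does not support this. It gives neither the number of cases with diabetes nor the effect on thresholds. If nerve dysfunction raises thresholds (an assumption), diabetes among the cases would work against the hypothesis of higher pain sensitivity in CMC OA, and the risk would be lost power.

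On matching, a reader might infer that clinic cases and volunteer controls will differ systematically in age. No such gap is shown, and age adjustment may be in an analysis plan that is not at hand. Recruiting controls to fixed age bands is a trade-off in a pilot with 20 per group and is not demanded here. What remains is loose terminology.

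**Conclusion.** The contradiction between script and criteria is established from the text and needs no assumption. Followed literally, the script labels women of 18 to 39 as age-matched controls, books callers under 40 as CMC OA subjects, and rejects volunteers with controlled diabetes, or with some autoimmune diseases, whom the criteria admit.

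That cases and controls face different diabetes rules is possible but not stated. It depends on question (f) not being put to clinic subjects. No bias figure is claimed for any part.

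The script should be corrected, because it governs cohort assignment and the correction is nearly free. The wording of age-matched is a minor clarification.

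**What to change.** 1. Split the script at age 40: respondents of 18 to 39 who clear (b) to (f) go to the young-healthy cohort, and those of 40 to 90 to the age-matched controls.
2. Apply the 40 to 90 limit in the CMC OA branch.
3. Reconcile question (f) with the all-groups exclusion on diabetes and autoimmune disease, and state that the same rule applies on the clinic route and the contact route. Which rule to adopt is for the investigators.
4. As a clarification, either state how age matching is done, or call the group same-age-range controls and use the age recorded in Session I as a covariate in the comparison of cases with controls.

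The cost is a change of wording in the protocol and the telephone script, with no added subjects or procedures. Using age as a covariate takes one degree of freedom (38 to 37 with 20 per group).

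While the CMC OA branch is open for editing, the investigators should also look at its requirement of no current or recently treated hand pain, which sits awkwardly with a study of symptomatic CMC OA. That is a separate matter from this point.
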